6. DOSAGE AND ADMINISTRATION

6.1. General Instructions and Procedures

The following will be used to prepare the vaccines:

- Ad26.HPV16: supplied in a single use vial (1×10^{11} vp/mL; 0.5 mL [extractable volume])
- Ad26.HPV18: supplied in a single use vial (1×10^{11} vp/mL; 0.5 mL [extractable volume])
- MVA.HPV16/18: supplied in a single use vial (5×10^8 Inf.U/0.5 mL; 0.5 mL [extractable volume])
- Placebo (0.9% saline): supplied in a single use vial (10 mL [filled volume])
- Diluent (Diluent 5, DS-TEC-79875): supplied in a single use vial (1 mL [extractable volume]) and to be added to the Ad26.HPV16 or Ad26.HPV18 vials for administration of the Ad26.HPV16 or Ad26.HPV18 vaccines at a dose of 5×10^{10} vp
- Diluent (tris-buffered saline [TBS] Diluent, DS-TEC-138030): supplied in a single use vial (1.5 mL [extractable volume]), 1.0 mL is to be added to the MVA.HPV16/18 vial for administration of the MVA.HPV16/18 vaccine at a dose of 2×10^8 Inf.U

For each participant, every vaccination with Ad26.HPV16 and/or Ad26.HPV18 will be 1.0 mL in volume. For the low dose of Ad26.HPV16 or Ad26.HPV18 (5×10^{10} vp), 0.5 mL of Ad26.HPV16 or Ad26.HPV18 and 0.5 mL of diluent 5 (DS-TEC-79875) will be mixed and administered as a single injection. For the high dose of Ad26.HPV16 or Ad26.HPV18 (1×10^{11} vp), two vials of 0.5 mL of Ad26.HPV16 or Ad26.HPV18 will be mixed and administered as a single injection.

The monovalent Ad26.HPV16 (5×10^{10} vp) and Ad26.HPV18 (5×10^{10} vp), vaccine components will be mixed at the pharmacy or at a designated product preparation area and administered as a single injection.

Vaccination with MVA.HPV16/18 at a dose of 2×10^8 Inf.U will be 0.5 mL in volume. Therefore, 1.0 mL of the diluent DS-TEC-138030 will be added to the vial of MVA.HPV16/18 (a concentration of 5×10^8 Inf.U per 0.5 mL) and mixed at the pharmacy or at a designated product preparation area, and 0.5 mL of the mix will be administered as a single injection.

To allow blinding, the volume of placebo vaccine will be the same as the volume of the corresponding Ad26.HPV16, Ad26.HPV18 or MVA.HPV16/18 vaccine.

The vaccines will be administered by intramuscular injection into the deltoid muscle of either arm by a blinded study vaccine administrator. Opposite arms should be used for the MVA injection unless local site reaction cannot be assessed reliably in the opposite arm. The arm in which the vaccine has been administered should be recorded in the eCRF. The injection site should be free from any injury, local skin problem, significant tattoo or other issue that might interfere with evaluating the arm after injection (eg, participants with a history of skin cancer must not be vaccinated at the previous tumor site). No local or topical anesthetic will be used prior to injection.

Blinding will be achieved by preparation of study vaccine by an unblinded pharmacist or other qualified study-site personnel with primary responsibility for study vaccine preparation and dispensing, and by the administration of vaccine in a masked syringe by a blinded study vaccine administrator. Full details of the study vaccine preparation will be provided in the Site Investigational Product and Procedures Manual.

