* If enrollment is slow for HPV18-infected participants, up to 8 HPV18-infected participants can be replaced by HPV16-infected participants, hence a minimum of 25 HPV18 participants is required. The decision will be taken during Step 5.

The study duration, from screening until the last follow-up visit, will be approximately 13.5 months per participant. The study consists of a screening period of up to 42 days (6 weeks), followed by vaccinations on Day 1 and Day 57, and follow-up visits up to 12 months after the first vaccination (target visit Day 366 ± 14 days).

PARTICIPANT POPULATION

Study participants must be healthy (on the basis of physical examination, medical history, vital signs measurement, and clinical laboratory tests performed at screening) women, aged ≥ 18 to ≤ 60 years on the day of signing the ICF, with HPV type 16 or 18 infection of the cervix determined within 8 weeks prior to screening or at the time of screening.

Women with cytology of HSIL or AIS or a colposcopy result of CIN2+ will be excluded. For the identification of eligible participants see [Figure 1](#).

Figure 1: Flow Chart for Identifying an HPV16 or HPV18 Infection Prior to Vaccination

DOSAGE AND ADMINISTRATION

The following will be used to prepare the study vaccines:

- Ad26.HPV16 (JNJ-63682918): supplied in a single use vial (1×10^{11} vp/mL; 0.5 mL [extractable volume])
- Ad26.HPV18 (JNJ-63682931): supplied in a single use vial (1×10^{11} vp/mL; 0.5 mL [extractable volume])
- MVA.HPV16/18 (JNJ-65195208): supplied in a single use vial (5×10^8 Inf.U/0.5 mL; 0.5 mL [extractable volume])
- Placebo (0.9% saline): supplied in a single use vial (10 mL [filled volume])
- Diluent (Diluent 5, DS-TEC-79875): supplied in a single use vial (1 mL [extractable volume]) and to be added to the Ad26.HPV16 or Ad26.HPV18 vials for administration of the Ad26.HPV16 or Ad26.HPV18 vaccines at a dose of 5×10^{10} vp
- Diluent (tris-buffered saline [TBS] Diluent, DS-TEC-138030): supplied in a single use vial (1.5 mL [extractable volume]), 1.0 mL is to be added to the MVA.HPV16/18 vial for administration of the MVA.HPV16/18 vaccine at a dose of 2×10^8 Inf.U

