3.2. Study Design Rationale

Rationale for Heterologous Immunizations

The study will use heterologous immunizations with replication-incompetent adenovirus- and MVA-vectored vaccine components that express HPV16 and HPV18 proteins. So far, in other programs conducted by the sponsor, such heterologous regimens have shown successful induction of strong, long-lived antigen-specific T cell responses. Strong T cell responses were seen in clinical studies with vectors expressing antigens from HIV-1, and Ebola.^{10,38} In the latter, heterologous regimens using an Ad26-based immunization, followed by immunization with MVA-based vectors within a timeframe of 8 weeks induced strong and durable T cell responses to Ebola antigens.

Supporting the Ad/MVA approach, strong HPV-specific T cell responses were observed in non-human primate studies conducted by the sponsor, using regimens that consisted of Ad26.HPV16 and Ad26.HPV18, each at 1×10^{11} vp followed with MVA.HPV16/18 at 1.79×10^8 Inf.U with an 8-week interval between immunizations. (see Section 1.1)

Rationale for Dose Selection

Safety data from clinical studies with other Ad26-vectored vaccines expressing different antigens are supportive of dosing the Ad26-based HPV vaccine components in this study at 5×10^{10} vp and 1×10^{11} vp. Both doses have been used in other Ad26 vaccine programs to successfully induce cellular immunity against the transgene, and results from the studies in non-human primates using 1×10^{11} vp of Ad26.HPV16 and 1×10^{11} vp of Ad26.HPV18 indicate that strong cellular immune responses were elicited at this dose.

The current study will use MVA.HPV16/18 at a dose of 2×10^8 Inf.U per immunization. In recombinant MVA-BN vaccine studies (HIV and therapeutic breast cancer vaccine [MVA-BN-HER2]), doses up to 5×10^8 TCID₅₀ were administered in varying schedules (refer to the IB for MVA.HPV16/18). In addition, an adequate safety profile has been established for the heterologous regimen of Ad26.ZEBOV and MVA-BN-Filo with doses up to 4×10^8 TCID₅₀.²

Rationale for Choice of Regimens

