14. STUDY VACCINE INFORMATION

14.1. Physical Description of Study Vaccine

Human replication-incompetent adenovirus-vectored vaccine candidates (manufactured and provided under the responsibility of the sponsor), as well as a MVA-based replication-incompetent vaccine (developed in collaboration with Bavarian Nordic A/S) (MVA-BN[®]) will be assessed in this study:

Ad26.HPV16 (JNJ-63682918)

Ad26.HPV16 is a recombinant replication-incompetent Ad26 vector encoding genetically modified HPV16 early (E2, E6 and E7) proteins.

For this study, Ad26.HPV16 will be formulated as a solution for intramuscular injection and supplied in a single use vial (1×10^{11} vp/mL; 0.5 mL [extractable volume]).

Ad26.HPV18 (JNJ-63682931)

Ad26.HPV18 is a recombinant replication-incompetent Ad26 vector encoding genetically modified HPV18 early (E2, E6 and E7) proteins.

For this study, Ad26.HPV18 will be formulated as a solution for intramuscular injection and supplied in a single use vial (1×10^{11} vp/mL; 0.5 mL [extractable volume]).

For Regimen 3 of this study, the monovalent Ad26.HPV16 and Ad26.HPV18 vaccine component will undergo mixing and will be given as a single injection; denoted by Ad26.HPV16/Ad26.HPV18 in this document.

MVA-mBN411B (JNJ-65195208)

MVA-mBN411B, referred to as MVA.HPV16/18 in this document, is a live vaccine which is non-replicating in human cells and encodes the same genetically modified HPV16 and HPV18 early (E2, E6 and E7) proteins.

For this study, MVA.HPV16/18 will be formulated as a suspension for intramuscular injection and supplied in a single use vial (5×10^8 Inf.U/0.5 mL; 0.5 mL [extractable volume]). The MVA.HPV16/18 vaccine will be administered at a dose of 2×10^8 Inf.U by mixing with the diluent DS-TEC-138030.

Placebo

Placebo will be supplied as sterile 0.9% saline for injection in 10 mL (filled volume) vials.

Diluent

Diluent 5 (20 mM histidine, 75 mM NaCl, 0.02% [w/v] tween-80, 5% [w/v] sucrose, 0.1 mM ethylenediaminetetraacetic acid [EDTA], 0.5% [v/v] ethanol, pH 6.5), DS-TEC-79875, will be supplied in a single use vial (1 mL [extractable volume]). This diluent is to be added to the Ad26.HPV16 or Ad26.HPV18 vials for administration of the Ad26.HPV16 or Ad26.HPV18 vaccines at a dose of 5×10^{10} vp.

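### Does the stated MVA.HPV16/18 dose of 2×10⁸ Inf.U fail to follow from the dilution volumes printed in the protocol?

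*Protocol*

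**What the plan says.** Section 6.1 and the Synopsis (Dosage and Administration) give the same preparation. The MVA.HPV16/18 vial has 5×10⁸ Inf.U per 0.5 mL with 0.5 mL extractable, and Section 14.1 repeats this: "Inf.U/0.5 mL; 0.5 mL [extractable volume". On the diluent, the lists of supplies read "1.0 mL is to be added to the MVA.HPV16/18 vial for administration of the MVA.HPV16/18 vaccine at a dose of" 2×10⁸ Inf.U. The text of Section 6.1 then says "Therefore, 1.0 mL of the diluent DS-TEC-138030 will be added to the vial of MVA.HPV16/18" "and 0.5 mL of the mix will be administered as a single injection". Section 14.1 states that the dose is reached at 2×10⁸ "Inf.U by mixing with the diluent DS-TEC-138030".

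No section states how much the MVA vial holds in total. A filled volume is printed only for placebo: "Placebo will be supplied as sterile 0.9% saline for injection in 10 mL (filled volume) vials". Sections 6.1 and 14.3 refer to the Site Investigational Product and Procedures Manual for preparation; that manual is not part of the protocol.

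For the high Ad26 dose, Section 6.1 says "two vials of 0.5 mL of Ad26.HPV16 or Ad26.HPV18 will be mixed and administered as a single injection".

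**The concern.** Section 6.1 states the dose and injection volume and then introduces the dilution with *Therefore*, as if the volumes were the derivation of the dose. A reader who puts the printed 0.5 mL into the sum gets 1.67×10⁸ Inf.U. In the same section the Ad26 doses come out exactly from 0.5 mL per vial, so the MVA figure stands out. Rounding is not declared either, and Section 3.2 prints the non-human-primate dose of the same product to three figures ("vp followed with MVA.HPV16/18 at" 1.79×10⁸ Inf.U).

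The administered dose is a basic fact in a first-in-human report, and this label applies to the second dose of every planned vaccine recipient: 2 × (4 + 10 + 10) = 48 by Tables 1 and 4. If the label were wrong, the report would describe the second dose inaccurately for all of them.

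**Working it through.** **Inputs (Section 6.1, repeated in the Synopsis and Section 14.1)**

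- Concentration: C = 5×10⁸ / 0.5 mL = 1×10⁹ Inf.U/mL
- Diluent added to the vial: 1.0 mL
- Volume injected: 0.5 mL (Synopsis and Section 6.1)
- Total vial content V: not printed, so it has to be assumed

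**Formula.** Because the diluent goes into the vial and only part of the mix is injected, dose = C × V / (V + 1.0) × 0.5.

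**With the only printed MVA volume, V = 0.5 mL:** 10⁹ × 0.5 / 1.5 × 0.5 = 1.67×10⁸ Inf.U, and 1.67 / 2.00 − 1 = −16.7%. The stated dose is not reproduced on this assumption. Reading 1.0 mL as the total mixed volume does not reproduce it either: 5×10⁸ / 1.0 × 0.5 = 2.5×10⁸.

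**Over a range of assumed contents:**

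| Assumed V (mL) | Dose (Inf.U) | Against 2×10⁸ |
|---|---|---|
| 0.50 | 1.67×10⁸ | −16.7% |
| 0.55 | 1.77×10⁸ | −11.3% |
| 0.60 | 1.88×10⁸ | −6.2% |
| 0.667 | 2.00×10⁸ | 0% |
| 0.70 | 2.06×10⁸ | +2.9% |
| 0.80 | 2.22×10⁸ | +11.1% |

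**Inverse.** V = D / (0.5×10⁹ − D).

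- The stated dose exactly: 2×10⁸ / 3×10⁸ = 0.667 mL
- Within 5% of it: 1.9×10⁸ / 3.1×10⁸ = 0.613 mL to 2.1×10⁸ / 2.9×10⁸ = 0.724 mL
- Values that print as 2×10⁸ at one significant figure (1.5 to just under 2.5×10⁸): 1.5 / 3.5 = 0.43 mL to just under 2.5 / 2.5 = 1.0 mL, which includes the no-overfill case

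**Ad26 comparison.** 0.5 mL × 1×10¹¹ vp/mL = 5×10¹⁰ vp, and two vials give 1×10¹¹ vp, both as stated. The contrast is weaker than it looks for the low dose. The supply lists in the Synopsis and Section 6.1, and Section 14.1, also describe Diluent 5 as going into the Ad26 vials. On that wording the low Ad26 dose depends on vial content in the same way.

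**Use in the analyses.** Section 11.2 uses only the counts 20 and 48. Sections 11.4 to 11.6 summarise by vaccine regimen and placebo, by HPV type or by infection type. Section 2.2 rules out formal hypothesis tests. The Inf.U value enters none of these.

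**The case for a change.** The strongest case for acting is that the protocol prints four numbers, presents three as the route to the fourth, and the three do not lead there. The same figures recur in the Synopsis and Sections 6.1 and 14.1, so this is not a stray typing error, and referring full details to a manual does not remove a mismatch among figures that the protocol prints itself. The 1.79×10⁸ Inf.U of Section 3.2 lies between the label and the no-overfill value, so a reader cannot tell on which side of it the trial dose falls. A clarifying sentence would cost almost nothing.

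What stands is that the dose cannot be verified from the protocol alone. The step from there to a wrong figure does not stand. It treats extractable volume as vial content, although the protocol uses extractable and filled volume as different terms. A vial described by what can be withdrawn may hold more, so 1.67×10⁸ is the result for a vial with no excess, not a dose that the protocol implies. The three-figure dose is a poor guide to the precision of the clinical label: every dose specified for this trial (5×10¹⁰, 1×10¹¹, 2×10⁸) has one significant figure. The Amendment 2 rationale also calls 1.79×10⁸ (given there in TCID₅₀) similar in strength to 2×10⁸, a difference of 0.21 / 2.00 = 10.5%.

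**Conclusion.** The protocol leaves one product input unprinted; it is not shown to contain a wrong dose. Depending on an assumed vial content of 0.50 to 0.80 mL, the injection holds 1.67 to 2.22×10⁸ Inf.U, and the true content is unknown from the document. Every value in that range agrees with the label at the precision in which it is printed.

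No change to the plan follows. Sites prepare this dose by volume, and the instruction is consistent wherever it appears: 1.0 mL into the vial, then 0.5 mL injected. If vials are filled alike, any offset from the label is common to all three vaccine regimens and leaves comparisons between them as they are. The placebo volume, the sample size statement, the analysis sets and the summaries do not depend on it.

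Anyone who wants to trace the label would have to reconcile vial content, diluent volume, injected volume and stated dose across the Synopsis, Sections 6.1 and 14.1, Tables 1 and 4 and the preparation manual. That is a clarification of product detail, and no view is taken here on which figure is right. The conclusion rests on the manual, which is not at hand, supplying the vial content or the nominal basis.

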6.2. Criteria for Postponement of Vaccination

A participant will not be given the first or second vaccination if she experiences any of the following events at the scheduled time for vaccination:

- Severe acute illness at the time of vaccination (this does not include minor illnesses such as diarrhea)
- Fever (body temperature $\geq 38.0^{\circ}\text{C}/100.4^{\circ}\text{F}$) at the time of vaccination.

If the vaccination visit cannot be rescheduled within the allowed window or the contraindications to vaccination persist, the sponsor should be contacted for further guidance.

For contraindications to vaccination that result in discontinuation of study vaccine, refer to Section 10.2.

7. STUDY VACCINE COMPLIANCE

Study vaccine will be administered intramuscularly by a blinded study vaccine administrator. The vaccine administrator will be a trained and qualified study nurse, medical doctor, or otherwise qualified health care professional. The date and time of each study vaccine administration will be recorded in the eCRF.

8. PRE-STUDY AND CONCOMITANT THERAPY

Pre-study specific therapies such as analgesic/antipyretic medications and non-steroidal anti-inflammatory drugs (NSAIDs), administered up to 30 days before first vaccination must be recorded at screening.

Concomitant therapies must be recorded from the time of ICF signature through 28 days after each vaccination, and additionally outside of these periods when associated with an SAE meeting the criteria outlined in Section 12.3.2. Information on concomitant use of herbal supplements or vitamins will not be collected.

Use of any experimental medication (including experimental vaccines other than the study vaccine) during the study is not allowed. Participants may not receive an investigational drug or use an investigation medical device within 30 days or receive an investigational vaccine within 6 months before the planned administration of the first dose of study vaccine.

Vaccination with licensed live-attenuated vaccines within 28 days of a study vaccination (ie, before and after) is not allowed. Other licensed vaccines (eg, tetanus, hepatitis A, hepatitis B, rabies) should be given at least 14 days before (or at least 14 days after) administration of study vaccine. If a vaccine is indicated in a post-exposure setting (eg, rabies or tetanus), it must take priority over the study vaccine.

Participants can receive medications such as acetaminophen, NSAIDs, or antihistamines as needed, although their use must be documented and use of these medications as routine prophylaxis prior to study vaccination is discouraged.

Chronic (longer than 10 days) or recurrent use of immunomodulators/suppressors, eg, cancer chemotherapeutic agents, systemic corticosteroids is prohibited during the study and within 6 months before the planned administration of the first dose of study vaccine (Note: Ocular, topical or inhaled steroids are allowed). Antineoplastic and immunomodulating agents, including herbal products, or radiotherapy are prohibited during the study and within 6 months before the planned administration of the first dose of study vaccine. If chronic use of such medicines becomes medically indicated during the course of the study for any participant, the sponsor

should be contacted. The participant should remain in the study but should not receive further study vaccination^a.

The sponsor must be notified in advance (or as soon as possible thereafter) of any instances in which prohibited therapies are administered.

9. STUDY EVALUATIONS

9.1. Study Procedures

9.1.1. Overview

The **TIME AND EVENTS SCHEDULE** summarizes the frequency and timing of immunogenicity, safety and virology measurements applicable to this study.

Evaluation of the safety/reactogenicity of the vaccine regimens will include laboratory assessments, physical assessment by study-site personnel, and participant reports on signs and symptoms following vaccinations. Additional unscheduled study visits may be required if in the investigator's opinion, further clinical or laboratory evaluation is needed.

Participants will be provided with a thermometer (to measure body temperature), ruler (to measure local injection site reactions), and participant diary to record body temperature and solicited local (at injection site) and systemic events.

The diary includes instructions on how to capture the data and grading scales to assess severity of the symptoms. The study staff is responsible for providing appropriate training to the participant to avoid missing or incorrect data (refer to Study Training Manual). The diary card will be reviewed by the study personnel at visits indicated in the **Time and Events Schedule**.

If the diary card review is missed, the diary card will be reviewed in the following visit. If a participant misses a vaccination, the diary covering the period after the missed vaccination does not have to be filled in.

The total blood volume to be collected during the study from each participant will be approximately 485 mL, which is considered acceptable based on the US Department of Health and Human Services Office for Human Research Protections, and the US FDA guidelines.^{49,50}

9.1.2. Visit Windows

Participants should be encouraged to come on the exact day planned and use the visit window only if necessary. For the following visits, windows will be allowed as indicated:

- Second vaccination: \pm 7 days

^a Depending on the time of the occurrence, any participant who receives a prohibited concomitant medication will not be included in the immunogenicity analyses.

- 7 days post-vaccination safety only visit: \pm 2 days
- 21 days post-Dose 2 vaccination safety, immunogenicity and virology visit: \pm 3 days
- 28 days post-vaccination safety only visit (telephone call): \pm 3 days
- 2 months post-Dose 2 vaccination safety and virology visit: \pm 5 days
- 6 months post-Dose 1 safety and virology visit: \pm 14 days
- 6 months post-Dose 2 vaccination safety, immunogenicity and virology visit: \pm 14 days
- 12 months post-Dose 1 safety, immunogenicity and virology visit: \pm 14 days

If a participant cannot be vaccinated within the allowed window, then that vaccination should not be administered. However, vaccination outside of the window (in particular if the window is missed due to a study pause) can be assessed on a case-by-case basis upon discussion between investigator and sponsor.

No visit windows are applicable for telephone calls to sentinel participants at 1 day post vaccination.

The timings of the second vaccination and of Visit 12 will be determined relative to the actual day of the first vaccination. The timing of visits 7, 8, 9, 10, 11 and 13 will be determined relative to the actual day of the second vaccination.

9.1.3. Screening Period (Days -42 to -2): Visit 1

Only participants complying with the inclusion and exclusion criteria specified in Section 4.1 and Section 4.2, respectively, will be included into the study. The investigator will provide detailed information on the study to the participants and will obtain written informed consent prior to each participant's participation in the study. All the procedures described in the [Time and Events Schedule](#) will only take place after written informed consent has been signed.

The following evaluations will be performed on participants to determine overall eligibility:

- Review of inclusion/exclusion criteria
- Demographic information
- Medical history and pre-study medications
- Physical examination including vital signs measurement (supine systolic and diastolic blood pressure, heart rate and oral temperature) and height and weight
- Healthcare provider-collected cervical sample for HPV16 and HPV18 PCR (If no recent HPV16 or HPV18 Cobas® test result is available at screening, the test will be performed on a stored cervical sample [if collected within a period of 8 weeks before screening] or on a new healthcare provider-collected sample)
- Self-collected cervico-vaginal sample for HPV16 and HPV18 PCR
- Serum β -hCG pregnancy testing (women of childbearing potential only)

- Blood sampling for HIV type 1 or type 2, hepatitis B and hepatitis C serology, and for safety laboratory testing (hematology and biochemistry)

General eligibility for this clinical study will be dependent on results of laboratory tests and the medical assessment. Study participants who qualify for inclusion based on the medical history, physical examination, and laboratory results will be contacted and scheduled for enrollment and first vaccination (Visit 2) within 42 days from signing the ICF.

Participants with laboratory values or vital signs not meeting eligibility criteria at the screening visit may have one repeat testing at the discretion of the investigator using an unscheduled visit during the 42-day screening period. Enrollment of a participant with laboratory values that are outside the laboratory normal reference ranges, and additionally within the limits representing FDA toxicity Grade 1 (see [Attachment 2](#)), is allowed if the investigator considers the values to be not clinically significant and reasonable for the population under study.

